#### 11.3.1.2 Tabulations of Treatment-Emergent Adverse Events

Treatment-emergent adverse events will be summarized by system organ class (SOC) and preferred term (PT) and by treatment group. The tables will display the total number of subjects reporting an AE, the percentage of subjects (%) with an AE, and the number of events reported. AEs will be presented by SOC sorted alphabetically and PT sorted in decreasing frequency of occurrence.

Summary tables will be prepared for the enrichment period and randomized-treatment period as outlined in [Table 8](#).

**Table 8 Tabulations of Treatment-Emergent Adverse Events**

	Enrichment Period Enrichment Period-Emergent Adverse Events (Safety-ENR Analysis Set)	Randomized Period Randomized- Treatment-Emergent Adverse Events (Safety-RT Analysis Data Set)	Gender-Specific Tabulations
Overview of Adverse Events by treatment group	X	X	
Adverse Events by causality (related/unrelated)	X	X	X
Adverse Events leading to death	X	X	
Adverse Events by intensity		X	X
SAEs	X	X	
Adverse Events leading to discontinuation	X	X	
Adverse Events with an incidence of at least 10% in any treatment group		X	X

	Enrichment Period Enrichment Period-Emergent Adverse Events (Safety-ENR Analysis Set)	Randomized Period Randomized- Treatment-Emergent Adverse Events (Safety-RT Analysis Data Set)	Gender-Specific Tabulations
Adverse drug reactions with an incidence of at least 10% in any treatment group		X	X

Supporting data listings will be provided for:

- All adverse events sorted by site and subject number
- All adverse events sorted by MedDRA Preferred Term
- Serious adverse events
- Adverse events leading to death
- Adverse events leading to discontinuation

### 11.3.2 Safety Laboratory Variables

#### 11.3.2.1 General Considerations

Laboratory variables will be grouped under “Haematology”, “Clinical Chemistry”, “Urinalysis”, or “Coagulation Factors”.

The reference ranges for laboratory values are presented in [Appendix 1](#).

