9.10.4 Safety Laboratory Variables

Laboratory test results and their change from baseline to end-of-trial will be summarised by treatment group for the Safety Analysis Set. The number and percent of subjects with clinically significant laboratory abnormalities will be presented. Shift tables from baseline to end-of-trial visit (categorised as low, normal and high) will be presented by treatment group.

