## Appendices

### Appendix 1 Markedly Abnormal Laboratory Safety Values, Vital Signs and ECGs

**Table A: Criteria for Markedly Abnormal Laboratory Test Results (Haematology)**

Variable	Units	Criteria for Markedly Abnormal	
		Low	High
Haemoglobin	g/L	≤ 80	≥ 200
Haematocrit	Ratio	≤ 0.30	≥ 0.54
Total WBC	10  /L	≤ 2.0	≥ 35.0
Total RBC	10  /L	≤ 3.0	≥ 6.2
MCV	fL	≤ 75	≥ 105
MCH	pg	≤ 25	≥ 35
MCHC	mmol/L	≤ 18.62	≥ 22.96
Basophils	%	≤ 0	≥ 1.5
Absolute Basophils	10  /L	≤ 0	≥ 2.0
Eosinophils	10  /L	< 3.0	Not applicable
Leucocytes	10  /L	< 2.5	> 15.0
Lymphocytes	10  /L	< 0.50	> 20.00
Monocytes	%	< 3.4	> 9.0
Absolute Neutrophil Count	10  /L	< 1	Not applicable
Platelets	10  /L	< 50	> 999

MCH: Mean corpuscular haemoglobin

MCHC: Mean corpuscular haemoglobin concentration

MCV: Mean corpuscular volume

RBC: Red blood cells

WBC: White blood cells

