**Table B: Criteria for Markedly Abnormal Laboratory Test Results (Clinical Chemistry)**

Variable	Units	Criteria for Markedly Abnormal	
		Low	High
AST (SGOT)	IU/L	Not applicable	> 5 x ULN AST(female): >155 AST(Male): >185
ALT (SGPT)	IU/L	Not applicable	> 5 x ULN ALT (female): >165 ALT(Male): >205
Alkaline phosphatase	IU/L	Not applicable	5 x ULN ALP (female): > 520 ALP(Male): >645
GGT	IU/L	Not applicable	> 3 x ULN
LDH	IU/L	Not applicable	> 3 x ULN
Globulin	g/dL		
Total bilirubin	mg/dL	Not applicable	≥ 1.5 x ULN
Direct bilirubin	mg/dL	Not applicable	≥ 8.55
Urea nitrogen	mmol/L	Not applicable	≥ 10.7
Creatinine	umol/L	Not applicable	Female: >168 Male: > 206
Glomerular Filtration Rate	mL/min	≤ 60	Not applicable
Total protein	g/L	≤ 45	≥ 90
Albumin	g/L	≤ 20	≥ 65
Potassium	mmol/L	≤ 2.5	≥ 6.5
Sodium	mmol/L	≤ 125	> 155
Chloride	mmol/L	≤ 90	≥ 115
Phosphorus	mmol/L	≤ 0.5	≥ 1.9
Calcium	mmol/L	≤ 1.75	≥ 3.13
Bicarbonate	mmol/L	≤ 15	≥ 34
Glucose	mmol/L	≤ 2.8	> 13.9
Magnesium	mmol/L	≤ 0.6	≥ 1.1
Total cholesterol	mmol/L	Not applicable	≥ 10.36
Triglycerides	mmol/L	Not applicable	> 5.65
CPK	U/L		> 850

ALT: Alanine transaminase

ALP: Alkaline phosphatase

AST: Aspartate transaminase  
CPK: Creatine phosphokinase  
GGT: Gamma glutamyl transferase  
IU:  
LDH: Lactate dehydrogenase  
SGOT: Serum glutamic oxaloacetic transaminase  
SGPT: Serum glutamic pyruvic transaminase  
ULN: Upper Limit Normal

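### SAP 11.3.2.1 presents Appendix 1 as the laboratory reference ranges, but it holds markedly abnormal criteria, and three entries (eosinophils, direct bilirubin, duplicate white-cell rows) are unusable as printed

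*SAP*

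**What the plan says.** SAP 11.3.2.1 groups the laboratory variables and then says "The reference ranges for laboratory values are presented in" Appendix 1. The appendix itself is titled "Markedly Abnormal Laboratory Safety Values, Vital Signs and ECGs", and the headings of Tables A and B describe markedly abnormal criteria in the same way.

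The entries at issue are:

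- Table A: "Eosinophils 10 9 /L < 3.0 Not applicable"
- Table A: "Leucocytes 10 9 /L < 2.5 > 15.0", alongside a separate Total WBC row with limits of 2.0 or below and 35.0 or above
- Table B: "Direct bilirubin mg/dL Not applicable ≥ 8.55"
- Table B: "Total bilirubin mg/dL Not applicable ≥ 1.5 x ULN"

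Protocol 9.10.4 plans shift tables from baseline to the end-of-trial visit, "categorised as low, normal and high", by treatment group. SAP 11.3.2.4 keeps shift tables only where needed. SAP 11.3.2.3 counts abnormalities by the investigator's three-category assessment. Serum sodium has its own section, SAP 11.2.1, with bands defined in Table 7.

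**The concern.** A low/normal/high table needs a lower and an upper limit of normal for each variable. The only source of ranges that the SAP gives a programmer is Appendix 1, whose limits are deliberately extreme. If they were used as ranges, moderately abnormal values would be classed as normal.

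The three entries are a separate problem, because they would mislead even if the appendix were used only for markedly abnormal flags. Eosinophils, direct bilirubin and white cells are all in the protocol's safety panel (Table 7-3). An eosinophil flag that fires for almost everyone, a direct bilirubin flag that adds nothing to the total bilirubin flag, and two answers for one white-cell count would each make such an output useless for that variable.

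**Working it through.** The plan has no figure of its own to reproduce here. The check compares Appendix 1 with the rest of the documents and with itself.

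**1. Are these reference ranges?**

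- Sodium: Appendix 1 gives 125 or below as low and above 155 mmol/L as high. The protocol's definition of terms puts the lower limit of normal at 135. SAP Table 7 grades 130 to <135 as mild and >125 to <130 as moderate. Read as a range, Appendix 1 would place both bands inside it.
- Enzymes: the limits are 5 x ULN. Dividing by 5 gives the ULN behind each one (female/male): AST 155/5 = 31 and 185/5 = 37; ALT 165/5 = 33 and 205/5 = 41; ALP 520/5 = 104 and 645/5 = 129 IU/L. The appendix therefore presupposes reference limits held somewhere else.

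So the label in 11.3.2.1 is wrong on the documents' own text, with no outside assumption.

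**2. Eosinophils.** Eosinophils are a subset of leucocytes. The appendix calls them low below 3.0 x10^9/L and calls all leucocytes low below 2.5. Anyone with leucocytes from 2.5 to just under 3.0 is not low on leucocytes but must be low on eosinophils.

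Share of leucocytes needed to escape the flag = 3.0 / leucocyte count:

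| Leucocytes (x10^9/L) | Eosinophil share needed |
|---|---|
| 3.0 | 100% |
| 4 | 75% |
| 7 | 43% |
| 11 | 27% |
| 15 (the row's own high limit) | 20% |

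Assume an eosinophil share of 1% to 10% and leucocytes of 4 to 15 (neither is given in the documents). Counts then run from 4 x 0.01 = 0.04 to 15 x 0.10 = 1.5, and every one is flagged low. With no high limit, no raised count can be flagged.

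**3. Direct bilirubin.** Direct bilirubin is part of total bilirubin. If direct is at least 8.55 mg/dL, so is total. Total is flagged at 1.5 x ULN, which stays at or below 8.55 for any total ULN up to 8.55/1.5 = 5.7 mg/dL. Up to that ULN, the direct row cannot flag a sample that the total row has not already flagged.

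The documents give no total-bilirubin ULN. The 1.5 mg/dL in Protocol 4.2.1 is part of a superseded eligibility limit, listed only for re-screening, so it is not used as a comparator. Across an assumed range:

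| Assumed total ULN (mg/dL) | 1.5 x ULN | 8.55 / (1.5 x ULN) |
|---|---|---|
| 1.0 | 1.50 | 5.7 |
| 1.2 | 1.80 | 4.75 |
| 1.5 | 2.25 | 3.8 |

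A possible explanation is a unit slip. With an assumed conversion of 1 mg/dL = 17.1 µmol/L (molar mass 584.66 g/mol), 8.55 µmol/L is 8.55/17.1 = 0.50 mg/dL. As printed, the limit equals 8.55 x 17.1 = 146 µmol/L. The urea nitrogen, creatinine and glucose rows are in SI units, which fits but does not prove it.

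**4. White cells.** Total WBC is markedly abnormal at 2.0 or below and at 35.0 or above. Leucocytes are so below 2.5 and above 15.0. The two rows disagree for counts above 2.0 and below 2.5, and for counts above 15.0 and below 35.0. A count of 20 is markedly high in one row and not in the other.

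**5. Which outputs could be affected?**

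- SAP 11.3.2.3, clinically significant abnormalities: investigator's assessment; Appendix 1 not used.
- SAP 11.2.1, hyponatraemia: Table 7 and fixed thresholds; Appendix 1 not used.
- Shift tables (Protocol 9.10.4, SAP 11.3.2.4): these need ranges, and the SAP points only to Appendix 1.
- Markedly abnormal flags: no SAP table is said to use them, but the appendix exists to define them.

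**The case against.** The strongest reply is that no planned output applies these cut-offs. The safety endpoint on clinically significant laboratory changes is tabulated from the investigator's assessment, and Protocol 7.1.3 works the same way. Sodium is covered in detail by SAP 11.2.1. The shift tables are now optional. A careful programmer would see the appendix title and the multiples of ULN and look elsewhere for normal ranges. The appendix also looks like a generic list: it includes LDH, magnesium, phosphorus, bicarbonate and total cholesterol, none of which is in the protocol's panel.

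Most of this stands, and it limits the point. A reader might infer that the safety output will be swamped by false low-eosinophil findings, or that the plan classes hyponatraemia as normal. The documents support neither: no planned table is tied to the eosinophil limit, and low sodium is graded from 135 mmol/L downwards in Table 7. Nor do they show how the errors arose. The eosinophil figure could be in the wrong column, carry the wrong sign or have the wrong unit; basophils and monocytes in Table A are given in percent. Moving it to the high column would also require reversing the inequality. The direct bilirubin unit slip is likewise an inference.

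The reply does not remove the error. The protocol commits to low/normal/high shift tables, the SAP leaves them open, and the one source of ranges it names would make them wrong if followed.

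**Conclusion.** The point holds as a minor SAP correction. The mislabelled cross-reference, the eosinophil floor above the leucocyte floor, and the conflicting white-cell rows are shown by the documents alone, given only that eosinophils are leucocytes and that the two white-cell rows name one quantity. The direct bilirubin row is redundant for any total ULN up to 5.7 mg/dL; the factor of 3.8 to 5.7 rests on the assumed ULN of 1.0 to 1.5 mg/dL. That every eosinophil count would be flagged rests on the assumed share and leucocyte range, with a wide margin (highest count 1.5 against a limit of 3.0).

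The effect is conditional: it reaches the report only if Appendix 1 is used for shift tables or for markedly abnormal flags. The efficacy analyses, the investigator-assessed abnormality counts and the sodium conclusions do not change.

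**What to change.** Before database lock:

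- In SAP 11.3.2.1, state that low/normal/high classification uses the central laboratory's reference ranges.
- Refer to Appendix 1 as markedly abnormal criteria, and state which outputs, if any, apply them.
- Check the eosinophil row (direction, column or unit) and the direct bilirubin unit against the source of the list, correct them, and have the safety physician confirm the values.
- Keep one leucocyte row.
- In the same pass, look at the empty globulin row and at the basophil rows, where a value of 0 counts as markedly low.

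The cost is one sentence and a few table entries in the SAP. No protocol amendment, new data or change to any efficacy or sodium analysis is needed.

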#### 11.3.2.2 Visits and Visit Windows

- Baseline for all laboratory analyses will be the values obtained at the last assessment before the subject received the first dose of the IMP.
- Treatment-emergent for laboratory data will be defined as specified for AEs in Section [11.3.1.1](#).
- End of trial will include the last post-baseline-ENR observation during the trial.
- Data will be analysed by planned visit using the visit-window structure as described in Section [3.1.5](#).

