Blood samples for assessment of coagulation factors will be collected at Visits 1, 4, 6 and 8.

The concentrations of the coagulation factors von Willebrand Factor (vWF) and Factor VIII (FVIII) were assessed in the phase 1 clinical trial, 000195, after both oral and intravenous administration of FE 201836. The results indicated that both vWF and FVIII were increased at high plasma concentrations of FE 201836. vWF started to increase at a plasma concentration of approximately 150 pg/mL FE 201836 and FVIII at a plasma concentration of approximately 200 pg/mL. Such high plasma concentrations are unlikely to be reached in the urological doses proposed for the present trial, however, vWF and FVIII will be measured as a safety precaution, and to ensure that these coagulation factors are not released in clinically significant amounts.

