## 6 Trial population

### 6.1 Demographics and Other Baseline Characteristics

#### 6.1.1 General Considerations

The trial has two baselines, one for the enrichment period (denoted baseline-ENR) including the latest data obtained before or at Visit 2, and one for the randomized-treatment period (denoted baseline-RT) including the latest data obtained before or at Visit 4 unless otherwise specified.

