#### **11.3.2.4 Laboratory Variable Changes Relative to Normal Range**

Shift tables will be presented on an as-needed basis only.

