#### **11.3.5.2 Physical examination**

- Physical examination findings will be categorized according to 'normal', 'abnormal, not clinically significant', and 'abnormal, clinically significant'.
- Baseline-ENR for the physical examination is the assessment at the Screening Visit, baseline-RT is the assessment at Visit 4, and End of Trial will include the last post-baseline-RT assessment during the trial.

Summary tables will be prepared by visit for the Safety-ENR analysis set, and by visit and treatment for the Safety-RT analysis set. Shift tables will be presented on an as-needed basis only.

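### SAP 11.3.2.2 sets one laboratory end-of-trial rule and one baseline for both safety sets, which does not suit Safety-RT, and SAP 11.3.2.4 makes the protocol's shift tables optional without declaring it

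*SAP*

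**What the plan says.** **End of trial.** SAP 11.3.2.2 (laboratory variables) has one rule: "End of trial will include the last post-baseline-ENR observation during the trial". SAP 6.1.1 defines two baselines, the first being "one for the enrichment period (denoted baseline-ENR) including the latest data obtained before or at Visit 2"; the second, baseline-RT, uses the latest data up to Visit 4. For physical examination, SAP 11.3.5.2 uses the randomised-period baseline instead: "End of Trial will include the last post-baseline-RT assessment during the trial".

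**Baseline.** SAP 11.3.2.2 sets the baseline for all laboratory analyses as the last assessment before the first dose of study drug. SAP 11.3.2.3 summarises change from baseline-ENR in Safety-ENR and change from baseline-RT in Safety-RT.

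**Shift tables.** Protocol 9.10.4: "Shift tables from baseline to end-of-trial visit (categorised as low, normal and high) will be presented by treatment group". SAP 11.3.2.4: "Shift tables will be presented on an as-needed basis only". SAP 14, which lists departures from the protocol, does not mention this one.

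**Coagulation factors.** Protocol 7.1.3.2: "Blood samples for assessment of coagulation factors will be collected at Visits 1, 4, 6 and 8". The same section reports that both factors rose at high plasma concentrations in phase 1, considers such concentrations unlikely at this trial's doses, and gives the purpose as "to ensure that these coagulation factors are not released in clinically significant amounts".

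**The concern.** The laboratory rules serve two analysis sets with different needs. Safety-ENR includes people who were never randomised, so a last value counted from Visit 2 onwards is natural there. Safety-RT is meant to show what happened on each randomised treatment, and a Visit 4 sample says nothing about that. No separate rule is given for Safety-RT, so a programmer following the text would credit a pre-randomisation value to a dose group. The two baseline statements add a second ambiguity, because two programmers could produce different change tables from the same data.

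The shift tables are the planned display that shows, by treatment group, how many subjects moved from normal to high. If they become optional, with no stated trigger and no entry in SAP 14, a protocol commitment can lapse without the reader of the report being told. This matters most for the two coagulation factors. SAP 11.3.2.1 sends the reader to Appendix 1 for reference ranges, but Appendix 1 has no row for either factor, and SAP 1.3.3 provides individual laboratory listings only when regulators require them.

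**Working it through.** The plan states no figure on this point, so there is none to reproduce. The check follows the rules through and then bounds their effect.

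**1. Can a pre-randomisation value qualify?** Coagulation samples are taken at Visits 1, 4, 6 and 8. Only Visit 1 is at or before Visit 2, so Visit 4 is post-baseline-ENR. With no Visit 6 or later sample, Visit 4 is the last observation.
- Against baseline-RT (also Visit 4), the change is Visit 4 minus Visit 4 = 0.
- Against the pre-drug baseline of 11.3.2.2 (Visit 1), the change is Visit 4 minus Visit 1. This covers the run-in and washout and likewise carries no information on the randomised dose.

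**2. Where does it enter?** SAP Table 4 sets the coagulation windows at analysis days 1 to 55 (Visit 6) and day 56 onwards (Visit 8). SAP 3.1.5 makes Visit 4 day 0. A Visit 4 value therefore cannot enter the Week 4 or Week 12 rows. It can enter the last-visit summary that SAP 1.3.1 requires for continuous data, and any shift table to end of trial. An early leaver's exit sample before day 56 does not reach the Week 12 row, so the last-visit row is the one that should represent such subjects.

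**3. How many subjects?** Inputs: 15% drop-out over 12 weeks (protocol 9.1), evenly spaced (protocol Appendix 2, section 4.3); Visit 5 at day 8 and Visit 6 at day 28 (protocol flow chart).
- Leaving before the first post-randomisation coagulation sample: 0.15 × 28/84 = 5.0%, or 15 of 300. With a constant hazard: 1 − 0.85^(28/84) = 5.3%.
- Safety-RT requires a safety assessment after randomisation (SAP 5.2.3). Subjects who leave before Week 1 and never return would mostly be outside the set: 0.15 × 1/12 = 1.25%. What remains is 0.15 × 3/12 = 3.75% of those randomised, or 3.75/98.75 = 3.8% of the set.
- Chemistry and haematology (first sample at day 8): 0.15 × 8/84 = 1.4%, most of whom the same exclusion removes.

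**4. Effect on the mean change from baseline-RT.** If a fraction f contributes zero, the last-visit mean change is multiplied by (1 − f).

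| Early leavers with no exit sample | f, all randomised | f, after the Safety-RT exclusion | Factor |
|---|---|---|---|
| all | 5.0% | 3.8% | 0.95 to 0.96 |
| half | 2.5% | 1.9% | about 0.98 |
| none | 0% | 0% | 1.00 |

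SAP 14 expects several dose groups to have 20 subjects or fewer. In a group of 20, 5.0% is one subject.

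**5. What remains without shift tables?** SAP 11.3.2.3 keeps the investigator's three-level grading: normal, abnormal not clinically significant, abnormal clinically significant. For the coagulation factors it is the remaining categorical laboratory display. It does not separate high from low, and it does not pair a subject's result with that subject's baseline. The Appendix 1 tables cover haematology, chemistry, and vital signs with body weight, and they give limits for marked abnormality rather than normal ranges.

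**The case against.** The strongest reply is that the main dose-level tables are sound. The randomised-period summaries are by visit, in Safety-RT, as change from baseline-RT, and the windows exclude Visit 4. The protocol asks early leavers to attend the end-of-trial visit (section 4.4 and the flow chart), and section 6.7 includes coagulation sampling there. If all attend, the effect is zero. All of this stands, and it limits the point to the last-visit summary and any shift table.

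Four stronger readings are tempting, and the documents do not support them.

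- A reader might infer that a rise in either factor would be hidden in group means. SAP 1.3.1 also requires the median, quartiles, minimum and maximum, so one outlying value in a small arm would show as the maximum. Protocol 7.1.3 requires clinically significant changes to be reported as adverse events.
- A reader might infer that values above range are not counted by dose. Under protocol 7.1.3, results outside the normal range are the ones graded abnormal, and protocol 9.10.1 summarises categorical safety data by treatment group. What is lost is direction and pairing with baseline.
- A reader might infer that the shift tables are deleted. They are made optional. The sponsor could add that SAP 14 closes by treating all remaining changes as clarifications. That does not fully answer the point: turning a commitment into an option is more than a clarification, and SAP 14 does name a comparable table change, the adverse-event threshold raised from 5% to 10%.
- A reader might extend the end-of-trial point to body weight, where SAP 11.3.5.1 has similar wording. The weight tables specified there count changes of more than 2 kg since the previous visit, so the rule has no consequence in them.

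**Conclusion.** The point holds in a limited form. The laboratory end-of-trial rule and baseline in SAP 11.3.2.2 do not suit Safety-RT, and they conflict with 11.3.2.3 and 11.3.5.2. For the coagulation factors, the last-visit mean change is attenuated by at most about 4 to 5%, and by nothing if every early leaver is sampled on exit. For chemistry and haematology the effect is close to nil. These figures assume the planned 15% drop-out, evenly spread; heavier drop-out before Week 4 without exit samples would raise them in proportion.

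The undeclared change to the shift tables is a separate matter of reporting and does not depend on drop-out. Neither part touches the primary inference or the by-visit safety rows. This is a minor correction, worth making because it is cheap and because "to ensure that these coagulation factors are not released in clinically significant amounts" is the protocol's own aim.

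**What to change.** - **SAP 11.3.2.2:** for Safety-RT, define end of trial as the last post-baseline-RT observation and baseline as baseline-RT. Keep the post-baseline-ENR rule and the pre-drug baseline for Safety-ENR.
- **SAP 11.3.2.4:** restore the protocol's low/normal/high shift tables by treatment group, at least for von Willebrand Factor, Factor VIII and clinical chemistry, using the central laboratory's normal ranges. If the sponsor prefers to leave them optional, name that change in SAP 14 with the reason and the trigger for producing them.

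The cost is a few sentences and a few standard tables from data already collected. The last-visit N becomes slightly smaller, because subjects with no post-randomisation sample no longer contribute.
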